#### Adverse events

All information obtained on adverse events will be displayed by treatment and subject.

The number and percentage of subjects with adverse events will be tabulated by body system and preferred term with a breakdown by treatment. A subject with multiple adverse events within a body system is only counted once towards the total of this body system and treatment.

The number and percentage of subjects with adverse events by maximum severity of adverse events will be tabulated by body system and preferred term with a breakdown by treatment.

The number and percentage of subjects with adverse events classified as related to study drug will be tabulated by body system and preferred term with a breakdown by treatment.

#### Asthma exacerbation AE

Adverse events related to asthma will also be analyzed separately using safety analysis set as detailed below.

SAP – Amendment 3

The number and percentage of subjects with any one AE preferred term corresponding to exacerbation of asthma will be summarized for each treatment group.

In addition the 'Time to first exacerbation' in days, will be presented graphically by treatment group using a Kaplan-Meier plot. A summary table the number and percentage who had exacerbations treated with antibiotics without steroids by treatment group will be presented together with the Kaplan-Meier plot. Descriptive statistics will also be summarized in a tabular format. Time to first exacerbation is defined as:

Start date of the AE – Date of first treatment dose + 1

A Cox proportional hazard model with previous exacerbations and baseline IgE will be performed to compare the time to first exacerbation between CJM112 and placebo.

Patients that have completed the study but did not experience any event during the study will be right censored at their EOS.

Patients that discontinued from the study but did not experience any event during the study will be right censored at the day of discontinuation.

Patients that are still ongoing in the study but did not experience any event by the time of data cut date then these subjects will be right censored at this date.

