3.1 Study design

This is a non-confirmatory, randomized, subject- and investigator-blinded, placebo-controlled, multi-center, parallel-arm study evaluating the efficacy of CJM112 on top of standard of care in patients with inadequately controlled moderate to severe asthma. This study will enroll approximately 110 patients. After an initial screening visit and run-in period of approximately 4 weeks, subjects eligible per inclusion and exclusion criteria at the baseline visit will be randomized (3:2) to receive Company Confidential Information CJM112 or matching placebo subcutaneously over 3 months during visits at the clinical study site. All baseline safety evaluation results must be available prior to the first dose. After the end of the treatment period, subjects will be followed for an additional 13 weeks. Site visits to administer dose and assess safety and efficacy will be scheduled as depicted in the figure below.

Figure 3-1 Study Design

Company Confidential Information

Screening and Run-In: Patients will provide informed consent and participate in an initial screening visit consisting of vital signs, physical exam, blood chemistry, ECG, pulmonary function tests, and ACQ. Subjects who meet all eligibility criteria at the screening visit will be dispensed a daily symptom diary and be asked to perform peak flow measurements over the approximately 4 week run-in period until the baseline visit.

Baseline: Subjects who qualify based on screening and run-in assessments will return for a baseline evaluation between Day -5 to Day -2. Subjects who meet all the applicable inclusion/exclusion criteria at screening and baseline will be randomized and will enter the treatment period. All screening and baseline assessments results must be available prior to randomization.

Treatment Period:

Company Confidential Information

At treatment period visits, safety, Company Confidential Information assessments will be performed. Safety assessments will include physical examinations, open ended health inquiry, ECGs, vital signs, standard clinical laboratory evaluations (hematology, blood chemistry, urinalysis), AEs and SAE monitoring.

Company Confidential Information

Company

Safety Follow-up: After completing the last dose Confidential Information, subjects will enter an additional follow-up period consisting of a visit on Day 92, Day 134 and an End of Study (EOS) visit on Day 176.

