3.2 Rationale of study design

This study is an exploratory, multi-center, randomized, subject- and investigator-blinded, placebo-controlled, parallel-group, phase IIa study with a 12-week treatment epoch.

Company Confidential Information

Rationale for population: An unmet medical need exists for patients with moderate or severe asthma who continue to demonstrate symptoms despite being on standard of care medications and are not eligible for other biologic therapies developed or in development for T2-high (allergic/eosinophilic) asthma (such as omalizumab and mepolizumab) because they have low circulating IgE and eosinophil levels at baseline.

Rationale for study design: In order to optimize the rigor and integrity of the study and minimize bias, a randomized, subject- and investigator-blinded parallel group study design is used. This design is well-established in respiratory clinical trials and enables the study treatment to be given for an appropriate and practical length of time to assess the efficacy and safety of the treatment.

Rationale for placebo control: The placebo arm controls for potential bias in efficacy and safety assessments. The study design includes a placebo control and not an active control because the study treatment will be added on top of standard of care therapy for each patient.

Rationale for run-in period: The run-in period will ensure subject's eligibility for the study at the baseline visit after their standard of care treatment has been adhered to during the run-in period and will minimize the potential for changes in key endpoints as a result of regression to the mean at the end of the study period.

Rationale for follow up period

Company Confidential Information

Hence, a follow up period is proposed after the last dose on study Day 85 to ensure patient safety, compliance with contraception requirements, and to assess for loss of efficacy of the investigational treatment

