3.3 Rationale for dose/regimen, route of administration and duration of treatment

The study participants will receive CJM112 300 mg or placebo s.c. injections 9 times during the 12 week treatment period: 5 weekly doses of 300 mg s.c. each (induction/loading) and 4 subsequent doses every 2 weeks (maintenance). This regimen is considered practical and feasible for this severe asthma population. A weekly loading dose regimen of 5 doses of 300 mg has been safe and well-tolerated with early evidence of efficacy in the ongoing clinical study in patients with hidradenitis suppurativa (CCJM112X2202)

Company Confidential Information . The 12 week treatment duration is considered adequate to demonstrate improvements in the key endpoints in patients with severe asthma based on published literature Wenzel et al 2016,

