6.3 Treatment assignment and randomization

At the Day 1 visit, all eligible patients will be randomized and treatment will be assigned via Interactive Response Technology (IRT). Randomization will be stratified by region (US, EU, and Rest of World). Standard of care practice for management of asthma may vary by region due to availability of inhalers; thus, we will stratify randomization by region. The IRT can be contacted via the interactive web response system (IWRS). The investigator or his/her delegate will contact the IRT after confirming that the subject fulfills all the inclusion/exclusion criteria.

The randomization numbers will be generated using the following procedure to ensure that treatment assignment is unbiased and concealed from subjects and investigator staff. A subject randomization list will be produced by the IRT provider using a validated system that automates the random assignment of subject numbers to randomization numbers. These randomization numbers are linked to the different treatment arms, which in turn are linked to medication numbers. A separate medication list will be produced by or under the responsibility of Novartis Drug Supply Management using a validated system that automates the random assignment of medication numbers to packs containing the investigational drug(s).

The randomization scheme for subjects will be reviewed and approved by a member of the Randomization Office.

Follow the details outlined in the Site Operations Manual regarding the process and timing of treatment assignment and randomization of subjects.

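### Minor: the Cox model for time to first exacerbation in SAP 7.2 leaves out region, the only randomisation stratum that Protocol 6.3 names

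*SAP*

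**What the plan says.** Protocol 6.3 states: "Randomization will be stratified by region (US, EU, and Rest of World"). The reason given is that standard of care may differ between regions with the inhalers available. No other stratification factor is named.

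SAP 7.2, under the asthma exacerbation heading, sets out the analysis on the safety set: "A Cox proportional hazard model with previous exacerbations and baseline IgE will be performed to compare the time to first exacerbation" between CJM112 and placebo. The two named covariates are the only ones. Region appears neither as a covariate nor as a stratum, and no reason is given. This paragraph carries no redaction mark.

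On follow-up time, the same section says: "Patients that have completed the study but did not experience any event during the study will be right censored at their EOS". Subjects who leave the study, or are still in it at a data cut, are censored at that date. Time to first exacerbation "will be presented graphically by treatment group using a Kaplan-Meier plot", with descriptive statistics beside it.

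**The concern.** A model usually accounts for the factors by which the trial was randomised. Here the sponsor chose region because background care may differ, and background care could plausibly affect how often patients exacerbate.

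If regional hazards do differ, two things follow from leaving region out:

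- **Estimate.** The hazard ratio is averaged over subjects with different baseline hazards and tends to move toward 1.
- **Test.** Stratified randomisation makes the regional mix alike in both arms, so regional differences add little to the chance difference between arms. The unstratified standard error does not credit that balance, so the test rejects too rarely.

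What is at stake is some precision in a supportive comparison with few expected events. False positives are not the issue.

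**Working it through.** **Inputs from the documents.** About 110 subjects randomised 3:2 (Protocol 3.1): 110 × 3/5 = 66 and 110 × 2/5 = 44. Three regions (Protocol 6.3). End of study on Day 176 (Protocol 3.1). Model terms from SAP 7.2.

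**The plan's own timeline.** Five weekly doses fall on Days 1, 8, 15, 22 and 29, and the four two-weekly doses on Days 43, 57, 71 and 85. Then 176 − 85 = 91 days = 13 weeks, which reproduces the stated follow-up.

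**Assumptions, because the documents show no event rate, target effect, alpha or regional split for this analysis.**

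- Constant placebo hazard, with 12-week placebo risk p of 8, 15 or 25%. By Day 176 the risk is 1 − (1 − p)^(176/84), which is 16, 29 and 45%.
- Dropout of 10%, hazard ratio 0.4 throughout, two-sided 5% Wald test.
- Regional hazards in the ratio 1/k : 1 : k. At k = 3 the extreme regions differ 9-fold.
- Regions either about equal (22:15, 22:15, 22:14) or sized 20/60/30, with exact 3:2 balance within each.
- 1,800 replicates per cell. The simulation error of one power figure is about √(0.65 × 0.35 / 1800) = 1.1 points.

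**(a) Previous exacerbations carry no regional information (25% risk).** Power, unstratified vs stratified:

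| Regions | k = 1 | k = 1.5 | k = 2 | k = 3 |
|---|---|---|---|---|
| Equal | 74 vs 74% | 72 vs 74% | 70 vs 76% | 66 vs 79% |
| 20/60/30 | 73 vs 73% | 75 vs 76% | 74 vs 76% | 75 vs 82% |

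With equal regions the gain is about 2, 6 and 13 points at k = 1.5, 2 and 3.

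**(b) Previous exacerbations are in the model and reflect the same hazard.** Each subject has a gamma frailty (variance 0.5). The prior-year count is Poisson with that subject's hazard, capped at 4, and IgE is noise. This is closer to the model that SAP 7.2 specifies:

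| Setting | k = 1 | k = 1.5 | k = 2 | k = 3 |
|---|---|---|---|---|
| 25% risk, equal | 67 vs 66% | 62 vs 62% | 64 vs 65% | 65 vs 66% |
| 25% risk, 20/60/30 | 66 vs 66% | 67 vs 67% | 67 vs 67% | 71 vs 72% |
| 15% risk, equal | 46 vs 46% | 47 vs 48% | 48 vs 50% | 49 vs 52% |
| 8% risk, equal | 26 vs 26% | 26 vs 27% | 27 vs 28% | 34 vs 35% |

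Before rounding, the gain is 0 to 3.5 points. With no regional difference (k = 1) the cost is at most 0.6 points, which is within simulation error.

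**Type I error** (hazard ratio 1, 25% risk, equal regions; simulation error about √(0.05 × 0.95 / 1800) = 0.5 points). Unstratified vs stratified:

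| Scenario | k = 1 | k = 2 | k = 3 |
|---|---|---|---|
| (a) | 4.8 vs 4.4% | 3.5 vs 5.6% | 2.1 vs 5.2% |
| (b) | 5.4 vs 5.0% | 3.7 vs 3.8% | 4.8 vs 5.6% |

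Leaving region out does not inflate the error rate. It is clearly conservative in (a) and shows no consistent pattern in (b).

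**Cross-check with log-rank tests.** With no covariates, regions of 40/40/30, 30% placebo risk by end of study, hazard ratio 0.5 and 1,500 runs, power is 42 vs 42% with equal regional hazards, 40 vs 43% at 0.5:1:2 and 33 vs 45% at 0.25:1:4. The pattern matches (a).

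**The case against.** **The effect is near zero in the model as specified.** This is the strongest point, and most of it stands. Previous exacerbations are already a covariate and probably carry much of any regional difference. Every patient must also be on at least medium-dose inhaled glucocorticoid plus another controller (Protocol 4.1), which may narrow the differences. A reader might infer from scenario (a) that the plan gives up 13 points of power. The documents do not support that: it needs a 9-fold hazard spread that the covariates miss entirely. What remains is that region is already recorded for randomisation, the sponsor itself gave the reason for using it, and adding it costs almost nothing.

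**A reader might infer that the test is invalid.** It is not, since rejection under the null is not raised.

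**A reader might infer that one hazard ratio to end of study is also a defect**, because 91 of 176 days (52%) follow the last dose and one stated purpose of follow-up is "to assess for loss of efficacy of the investigational treatment". If an on-treatment hazard ratio of 0.50 vanished abruptly at Day 99 (85 + 14), the full-period value would be 0.67 to 0.70. The documents do not make this an error, for these reasons:

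- The analysis is of adverse events on the safety set, and adverse events are collected to the end-of-study visit (Protocol 9.1).
- Protocol 3.2 does not tie loss of efficacy to exacerbations. SAP 6.2 schedules spirometry at follow-up visits 201 and 299, which can serve that aim.
- The Kaplan-Meier plot already shows the treatment period.
- The pharmacokinetic text is redacted, so nothing visible shows when, or whether, an effect wanes. If it persists there is no dilution, and the full period has more power than a Day 92 cut (54 vs 35% at 25% risk and hazard ratio 0.5).
- Exploratory sections are redacted and may hold a treatment-period estimate.
- A fixed Day 92 cut would not isolate treatment, because early discontinuers contribute off-drug time before it (Protocol 7.1 and 7.2).

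**Conclusion.** The point holds as a minor one, for region only. The visible Cox model does not reflect the single factor by which the trial randomises, and no reason is given. The likely benefit of including region is about 0 to 3.5 points of power. It is larger only if regional hazards differ strongly and previous exacerbations do not capture the difference. The cost is under 1 point if regions do not differ.

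These sizes rest on assumed event rates, a hazard ratio of 0.4, assumed regional spreads and sizes, and exact balance within region. None of these comes from the documents. That region is absent from the model does not depend on them.

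This is a supportive safety-set analysis in a trial that calls itself non-confirmatory. It does not touch the FEV1 primary result, whose model is redacted and is not judged here.

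**What to change.** Amend SAP 7.2 before unblinding so that the Cox model is stratified by region (US, EU, Rest of World), with previous exacerbations and baseline IgE kept as covariates. Commit to stratification outright, with no rule for switching to a region covariate if events turn out to be few. No switch is needed: a region without events simply adds nothing to the stratified partial likelihood, and the treatment effect is still estimated from the others. SAP 1.4 foresees at least two interim analyses, and the documents do not show whether one has taken place. If unblinded exacerbation data have already been seen, the amendment should say so.

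Leave the censoring at end of study as it is. If a view of the treatment period is wanted, Kaplan-Meier estimates by arm at Day 92 could be added as a descriptive item. That is optional and corrects nothing.

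The cost is one strata term and a short amendment, with no new data.

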#### ClinicalTrials.gov and EudraCT

For the legal requirements of ClinicalTrials.gov and EudraCT, two required tables on treatment emergent adverse events which are not serious adverse events with an incidence greater than 2 % and on treatment emergent serious adverse events and SAE suspected to be related to study treatment will be provided by system organ class and preferred term on the safety set population.

If for a same patient, several consecutive AEs (irrespective of study treatment causality, seriousness and severity) occurred with the same SOC and PT:

- a single occurrence will be counted if there is  $\leq 1$  day gap between the end date of the preceding AE and the start date of the consecutive AE
- more than one occurrence will be counted if there is > 1-day gap between the end date of the preceding AE and the start date of the consecutive AE.

For occurrence, the presence of at least one SAE / SAE suspected to be related to study treatment / non-SAE has to be checked in a block e.g., among AE's in a  $\leq$  1-day gap block, if at least one SAE is occurring, then one occurrence is calculated for that SAE.

The number and percent of deaths will be provided by treatment group.

#### Other safety evaluations

#### **Immunogenicity**

All immunogenicity results will be listed by subject and visit/time.

#### **Pregnancy**

Pregnancy test results will be listed by treatment group, subject and visit/time.

# 7.3 Graphical presentation

Company Confidential Information

# 10 Appendix 1: Historical clinical trials use in meta-analyses of informative prior of FEV1.

Table 10-1 Mean change from baseline of FEV1 (L) at Week 12 in the placebo group of the selected six studies

Selected study	Selected population	n	FEV1 change from baseline (L)	SE
AIN457D2204	IgE < 100 IU/ml	7	0.007	0.098
QBX258X2201	IgE <400 IU/ml	9	0.015	0.116
QAW029A2206	overall	136	0.038	0.039
QAW039A2214	non-atopic	93	0.03	0.029
Dupilumab				
(Wenzel et al, 2016)	eos count < 300	71	0.1	0.040
Brodalumab				
(Busse et al, 2013)	overall	76	0.056	0.036
